## 3.3 Additional Efficacy Endpoints

Additional efficacy endpoints are described in Section 9.5.

### 3.4 Safety Endpoints

• ALT elevations of the National Cancer Institute (NCI) Common Terminology Criteria for Adverse Events (CTCAE) v4.03 Grade 1, 2, 3, or 4 during the Treatment Period with ALT grade increased from baseline for each subject in the Safety Analysis Set;

- Post-nadir ALT elevation > 3 × upper limit of normal (ULN) with total bilirubin > 2 × ULN during the Treatment Period for each subject in the Safety Analysis Set;
- Treatment-emergent hepatic decompensation/hepatic failure events for each subject in the Safety Analysis Set;
- Treatment-emergent AEs leading to discontinuation of study treatment for each subject in the Safety Analysis Set;
- Treatment-emergent SAEs for each subject in the Safety Analysis Set.

These endpoints, along with additional safety endpoints based on AEs, laboratory data, and vital signs are included in Section 10.2, Section 10.3, and Section 10.4, respectively.

## 4.0 Analysis Populations

The following population sets will be used for the analyses.

The ITT population is defined as all enrolled subjects who received at least 1 dose of study treatment. The ITT population will be used for the primary efficacy analysis and other secondary efficacy analyses.

The mITT-VF population is defined as all enrolled subjects who received at least 1 dose of study treatment, excluding those who did not achieve SVR12 for reasons other than virologic failure (i.e., those with HCV reinfection, those who did not achieve SVR12 due to early premature discontinuation of study treatment, and those who were missing HCV RNA data in the SVR12 window after backward imputation). The mITT-VF population will be used for the key secondary efficacy analysis.

The Safety Analysis Set consists of all subjects who received at least 1 dose of study treatment.

## 5.0 Subject Disposition

The number and percentage of subjects who failed to enroll in the study (i.e., failed to receive at least 1 dose of study treatment) for any reason and for each reason, will be summarized for the set of all subjects who failed to enroll.

A summary of subject accountability will be provided where the number of subjects in each of the following categories will be tabulated overall and by investigator:

- Subjects enrolled/treated (i.e., received at least 1 dose of study treatment) in the study;
- Subjects who completed study treatment;
- Subjects who prematurely discontinued study treatment;
- Subjects who completed the study;
- Subjects who prematurely discontinued from the study;
- Subjects in each analysis population (ITT, mITT-VF, and Safety Analysis Set).

The number and percentage of subjects in the Safety Analysis Set who discontinued study treatment will be summarized by primary reason (per eCRF). A similar summary will be provided for discontinuations from the study. The number and percentage of subjects in the Safety Analysis Set with reported study treatment interruptions will be summarized.

Protocol deviations as described in Appendix A will be summarized for the Safety Analysis Set by the number and percentage of subjects in each category and in at least one category, including a list of subject numbers for each category.

## 6.0 Study Treatment Duration and Compliance

The duration of study treatment will be summarized for the Safety Analysis Set. Duration of treatment is defined for each subject as the last study treatment dose date minus the first study treatment dose date plus 1 day.

Descriptive statistics (number of subjects, mean, standard deviation, median, Q1 and Q3 of inter-quartile range, minimum, and maximum) will be presented.

Treatment duration also will be summarized with frequencies and percentages using the following categories:

- 1 to 15 days, 16 to 35 days, 36 to 55 days,  $\geq$  56 days;
- < 52 days,  $\geq 52$  days.

Treatment compliance will be summarized for the ITT population. At each visit (starting with the Week 4 visit) during the Treatment Period, the total number of tablets dispensed and returned is recorded. The compliance for study treatment (GLE/PIB) during the Treatment Period will be calculated as the percentage of tablets taken relative to the total tablets expected to be taken. The total number of tablets expected to be taken will be equal to the total number of tablets that should have been taken per the protocol (i.e., 3 tablets per day) for the duration that the subject was in the Treatment Period (date of the last dose of study treatment date of first dose of study treatment + 1). Study treatment interruptions recorded on the eCRF will not be subtracted from the duration. If the number of tablets returned is not available for one or more of the bottles dispensed to a subject, then compliance will not be calculated for that subject.

A subject is considered to be compliant if the percentage is between 80% and 120%. Compliance will be calculated for each subject and summarized with the number of subjects, mean, standard deviation, median, Q1 and Q3 of inter-quartile range, minimum, and maximum. The percentage of compliant subjects will be summarized based on the data as observed.

# 7.0 Demographics, Baseline Characteristics, Medical History, and Prior/Concomitant Medications

Demographics, baseline characteristics, medical history, and previous, concomitant and post-treatment medications will be summarized for the ITT population. Demographics and baseline characteristics will also be summarized for the mITT-VF population. Categorical

variables will be summarized with the number and percentage of subjects; percentages will be calculated based on the number of non-missing/non-unknown observations. Continuous variables will be summarized with descriptive statistics (number of non-missing/non-unknown observations, mean and standard deviation, median, Q1 and Q3 of inter-quartile range, minimum, and maximum).

#### 7.1 Demographics and Baseline Characteristics

Demographics and baseline characteristics will be summarized for the following groups: adolescents (age < 18 years), adults (age  $\geq$  18 years), and overall. Summaries of demographics and baseline characteristics will also be presented for the following groups: current/recent PWID subjects and former/non-PWID subjects using PWID Status Classification 1 (see definitions below), subjects with a history of opiate substitution therapy use that was ongoing at start of study treatment, and subjects with either no history of opiate substitution therapy use or a history of opiate substitution therapy use that was not ongoing at start of study treatment.

Continuous demographic variables include age, weight, height, and body mass index (BMI). Categorical demographic variables include sex (male or female), race (white, black/African-American, Asian, [further categorized as Japanese, Chinese, Korean, Taiwanese, or other Asian], American Indian/Alaska native, or native Hawaiian/other Pacific Islander; black or non-black), ethnicity (Hispanic/Latino or not Hispanic/Latino), age (< 18, 18 to < 40, 40 to < 65, 65 to < 75,  $\geq$  75 years; < 18 or  $\geq$  18 years; < 65 or  $\geq$  65 years; < 75 or  $\geq$  75 years), BMI (< 30 or  $\geq$  30 kg/m^2), country, geographic region (North America, Europe, or rest of world [ROW]), tobacco use (current, former, never, or unknown), and alcohol use (current, former, never, or unknown).

Continuous baseline characteristics include baseline log10 HCV RNA level, ALT, aspartate aminotransferase (AST), bilirubin (total, direct, and indirect), alkaline phosphatase, serum creatinine, creatinine clearance (Cockcroft-Gault calculation), estimated glomerular filtration rate (eGFR; modification of diet in renal disease [MDRD]

equation), platelet count, serum albumin, international normalized ratio (INR), homeostasis model of assessment insulin resistance (HOMA-IR), GGT, LDL, HDL, FibroTest score, FibroScan score, aspartate aminotransferase to platelet ratio index (APRI), Fibrosis-4 (FIB-4), CD4 (for HCV/HIV co-infected subjects), estimated acute HCV infection duration, and time since acute HCV infection diagnosis.

Categorical baseline characteristics include:

- HCV genotype (GT) (1, 2, 3, 4, 5, or 6) and available subtype (as determined by the central laboratory);
- HCV genotype (GT) (1, 2, 3, 4, 5, or 6) and available subtype (final HCV genotype and subtype as defined in Section 9.7);
- Cirrhosis status (cirrhotic, non-cirrhotic, or unknown test results indeterminate);
- Baseline Child-Pugh score (for cirrhotic subjects or subjects with cirrhosis status unknown; 5, 6, or > 6)
- Screening Child-Pugh score (for cirrhotic subjects or subjects with cirrhosis status unknown; 5, 6, or > 6)
- Baseline fibrosis stage (equivalent to Metavir F0 F1, F2, F3, or F4);
- Baseline HCV RNA level (< LLOQ or ≥ LLOQ; < 800,000 or ≥ 800,000 IU/mL; < 1,000,000 or ≥ 1,000,000 IU/mL);

- Baseline ALT (≤ ULN, > ULN to ≤ 3 × ULN, > 3 × ULN to ≤ 5 × ULN, > 5 × ULN to ≤ 10 × ULN, or > 10 × ULN);
- Baseline total bilirubin (< 34.2 or  $\ge$  34.2  $\mu$ mol/L);
- Baseline creatinine clearance (<  $60, \ge 60$  to <  $90, \text{ or } \ge 90$  mL/min);
- Baseline eGFR (< 90 or  $\geq$  90 mL/min/1.73 m^2);
- Baseline platelet count (< 100 or  $\ge$  100 × 10^9/L; < 150 or  $\ge$  150 × 10^9/L);
- Baseline serum albumin (< 35 or  $\geq$  35 g/L);
- Baseline APRI ( $\leq 1, > 1$  to  $\leq 2$ , or > 2);
- Baseline HOMA-IR (< 2 or  $\geq$  2 mU × mmol/L);
- Baseline FibroTest (< 0.75 or  $\geq$  0.75);

- Baseline FIB-4 (< 1.45,  $\ge 1.45$  to  $\le 3.25$ , or > 3.25);
- Baseline AST/ALT ratio ( $\leq 1 \text{ or } > 1$ );
- Baseline HCV/HIV co-infection status (HCV mono-infected or HCV/HIV-1 co-infected);
- History of diabetes (yes or no);
- History of prior HCV infection (yes or no);
- History (i.e., started prior to start of study treatment) of non-prescribed illicit drug use (yes, ongoing as of the end of study participation; yes, last dose after last dose of study treatment; yes, last dose during study treatment period; yes, last dose less than 6 months prior to start of study treatment; yes, last dose more than 12 months prior to start of study treatment; yes, last dose more than 12 months prior to start of study treatment; yes, last dose unknown; or no);
- History (i.e., started prior to start of study treatment) of non-prescribed illicit injection drug use (yes, ongoing as of the end of study participation; yes, last dose after last dose of study treatment; yes, last dose during study treatment period; yes, last dose less than 6 months prior to start of study treatment; yes, last dose 6 to 12 months prior to start of study treatment; yes, last dose more than 12 months prior to start of study treatment; yes, timing of last dose unknown; or no);
- PWID Status Classification 1 PWID classification defined with respect to study treatment start (current/recent PWID or former/non-PWID; current PWID, recent PWID, former PWID, or non-PWID)
  - Current/recent PWID defined with non-prescribed illicit injection drug use as:
    - yes, started prior to start of study treatment and ongoing as of end of study participation (Current);
    - yes, started prior to start of study treatment with last dose after last dose of study treatment (Current);
    - yes, started prior to start of study treatment with last dose during study treatment period (Current);
    - yes, started prior to start of study treatment with last dose less than 6 months prior to start of study treatment (Recent);

- yes, started prior to start of study treatment with last dose 6 to 12 months prior to start of study treatment (Recent).
- Former/Non-PWID defined with non-prescribed illicit injection drug use as:
  - yes, started prior to start of study treatment with last dose more than 12 months prior to start of study treatment (Former);
  - yes, started prior to start of study treatment and timing of last dose unknown (Former);
  - yes, started during study treatment period (Non-PWID);
  - yes, started after last dose of study treatment (Non-PWID);
  - no (Non-PWID).
- PWID Status Classification 2 PWID classification defined with respect to study treatment period (current/recent PWID or former/non-PWID; current PWID, recent PWID, former PWID, or non-PWID)
  - Current/Recent PWID defined with non-prescribed illicit injection drug use as:
    - yes, started prior to start of study treatment and ongoing as of end of study participation (Current);
    - yes, started prior to start of study treatment with last dose after last dose of study treatment (Current);
    - yes, started prior to start of study treatment with last dose during study treatment period (Current);
    - yes, started prior to start of study treatment with last dose less than 6 months prior to start of study treatment (Recent);
    - yes, started prior to start of study treatment with last dose 6 to 12 months prior to start of study treatment (Recent);
    - yes, started during study treatment period (Current).
  - Former/Non-PWID defined with non-prescribed illicit injection drug use as:
    - yes, started prior to start of study treatment with last dose more than 12 months prior to start of study treatment (Former);

- yes, started prior to start of study treatment and timing of last dose unknown (Former);
- yes, started after last dose of study treatment (Non-PWID);
- no (Non-PWID).
- PWID Status Classification 3 PWID classification defined with respect to study participation (current/recent PWID or former/non-PWID; current PWID, recent PWID, former PWID, or non-PWID)
  - Current/Recent PWID defined with non-prescribed illicit injection drug use as:
    - yes, started prior to start of study treatment and ongoing as of end of study participation (Current);
    - yes, started prior to start of study treatment with last dose after last dose of study treatment (Current);
    - yes, started prior to start of study treatment with last dose during study treatment period (Current);
    - yes, started prior to start of study treatment with last dose less than 6 months prior to start of study treatment (Recent);
    - yes, started prior to start of study treatment with last dose 6 to 12 months prior to start of study treatment (Recent);
    - yes, started during study treatment period (Current);
    - yes, started after last dose of study treatment (Current).
  - Former/Non-PWID defined with non-prescribed illicit injection drug use as:
    - yes, started prior to start of study treatment with last dose more than 12 months prior to start of study treatment (Former);
    - yes, started prior to start of study treatment and timing of last dose unknown (Former);
    - no (Non-PWID).

- History of opiate substitution therapy use (yes, ongoing at start of study treatment; yes, less than 6 months prior to start of study treatment; yes, 6 to 12 months prior to start of study treatment; yes, more than 12 months prior to start of study treatment; yes, timing of last dose unknown; or no);
- Acute HCV infection criteria met (a. yes, negative anti-HCV antibody, HCV RNA and/or HCV core antigen followed by a positive HCV RNA or HCV core antigen all within an 8-month period prior to Screening; b. yes, negative anti-HCV antibody, HCV RNA and/or HCV core antigen followed by a positive HCV RNA or HCV core antigen all within an 11-month period prior to Screening; AND risk behavior within 6 months prior to positive HCV RNA or HCV core antigen; c. yes, clinical signs and symptoms compatible with acute hepatitis (ALT > 5 × ULN and/or jaundice) in the absence of a history of chronic liver disease or other cause of acute hepatitis and positive HCV RNA or HCV core antigen all within an 8-month period prior to Screening; AND risk behavior within 6 months prior to positive HCV RNA or HCV core antigen all within an 8-month period prior to Screening; AND risk behavior within 6 months prior to positive HCV RNA or HCV core antigen; d. yes, negative anti-HCV antibody with a positive HCV RNA or HCV core antigen within a 5-month period prior to Screening; or, e. no criteria met);
- Risk behavior for acute HCV infection (shared drug-injection equipment, shared non-injection drug use equipment, unprotected sexual activity with multiple partners, unprotected sexual activity with other male(s), risky tattoos or body piercings, shared personal items possibly contaminated with blood, healthcare worker with occupational exposure, or other behavior);
- Grouped risk behavior for acute HCV infection Grouping 1 (contaminated needle or IV drug use, contact with infected individual, occupational exposure, or other behavior);
- Grouped risk behavior for acute HCV infection Grouping 2 (drug use, sexual transmission, contact by contaminated objects, occupational, or other behavior);
- Estimated acute HCV infection duration (< 3 months, ≥ 3 months to

   < 6 months, or ≥ 6 months) across all and by each acute HCV infection criteria;

- Time since acute HCV infection diagnosis (< 3 months or  $\geq$  3 months);

- Baseline HIV-1 treatment status (for HCV/HIV co-infected subjects: HIV Treatment-Naïve or HIV-Treated);
- Baseline CD4+ T-cell count (for HCV/HIV co-infected subjects: < 200, 200 to < 350, 350 to < 500, or  $\ge 500$  cells/mm^3);
- Baseline plasma HIV-1 RNA (for HCV/HIV co-infected subjects: < 20 or  $\geq$  20 copies/mL).

Estimated acute HCV infection duration (days) is an estimate of how long a subject has been infected with HCV at the time of start of study treatment. The derivation differs slightly for each acute infection criteria category. Derivations used for this study were adapted from derivations used in the Matthews (2021) and Martinello (2019) articles. For each definition below, the most recent (i.e., closest to study treatment start date) negative HCV test of those specified and the earliest (i.e., furthest from study treatment start date) positive HCV test of those specified will be used.

- a. For acute infection criteria (a), estimated infection start date is defined as the midpoint between the HCV negative test and HCV positive test.
- b. For acute infection criteria (b), estimated infection start date is defined as the midpoint between the HCV negative test and HCV positive test.
- c. For acute infection criteria (c), estimated infection start date is defined as 6 weeks (42 days) prior to the date of the HCV positive test.
- d. For acute infection criteria (d), estimated infection start date is defined as6 weeks (42 days) prior to the date of the HCV positive test.

The estimated duration of infection is defined as (study treatment start date estimated infection start date) + 1, in days.

Because a subject may qualify for more than one definition of acute HCV infection, the estimated infection duration will be determined using the following priority order for each subject: acute infection criteria (d), criteria (a), criteria (b), or criteria (c). For example, if a subject meets acute infection criteria (a) and (c), the estimated infection duration

associated with criteria (a) will be used. This prioritization will also be used to determine which acute HCV infection criteria each subject's estimated duration of infection is summarized under.

For categorization of the estimated infection duration, 1 month 31 days (e.g., 3 months is 93 days and 6 months is 186 days).

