• Negative anti-HCV antibody, HCV RNA and/or HCV core antigen followed by a positive HCV RNA or HCV core antigen all within an 11-month period prior to Screening; AND risk behavior for HCV infection within 6 months prior to positive HCV RNA or HCV core antigen;

OR

 Clinical signs and symptoms compatible with acute hepatitis (ALT > 5 × ULN and/or jaundice) in the absence of a history of chronic liver disease or other cause of acute hepatitis and positive HCV RNA or HCV core antigen all within an 8-month period prior to Screening; AND risk behavior for HCV infection within 6 months prior to positive HCV RNA or HCV core antigen;

OR

- Negative anti-HCV antibody with a positive HCV RNA or HCV core antigen within a 5-month period prior to Screening.
- 6. Negative test result for hepatitis B surface antigen (HBsAg).
- 7. No evidence of chronic HCV infection for this HCV infection.
- 8. No known active SARS-CoV-2 infection. All subjects should undergo viral testing to rule out SARS-CoV-2 infection at Screening. Subjects with active SARS-CoV-2 infection may only rescreen after they meet the following SARS-CoV-2 infection viral clearance criteria:
 - At least 10 days since first polymerase chain reaction (PCR) test result have passed in asymptomatic patients; or 10 days have passed since symptom onset and at least 24 hours since resolution of fever without use of antipyretics and other symptoms improvement.
- 9. Subject with HCV/human immunodeficiency virus 1 (HIV-1) co-infection must also meet the following criteria:
 - Naïve to HIV treatment:
 - Must have a cluster of differentiation 4 (CD4+) count ≥ 500 cells/mm³ (or CD4+ % ≥ 29%) at Screening;
 - Have no plan to initiate HIV-1 antiretroviral therapy (ART) treatment while participating in this study.
 - On a stable, qualifying HIV-1 ART regimen for at least 8 weeks prior to Screening:
 - Must have CD4+ count ≥ 200 cells/mm³ (or CD4+ % ≥ 14%) at Screening, and plasma HIV-1 RNA < 50 copies/mL at Screening (by the COBAS® Ampliprep/COBAS® Taqman HIV-1 Test, v 2.0).
 - The HIV-1 ART regimen must include at least 1 of the following:
 - Raltegravir orally (per os) (PO) twice a day (BID)
 - Dolutegravir PO QD or BID
 - Rilpivirine PO QD
 - Elvitegravir/cobicistat PO QD
 - Bictegravir PO QD

In addition to the above medications, subjects may take a nucleoside/nucleotide reverse transcriptase inhibitor backbone containing any of the following:

- Tenofovir disoproxil fumarate PO QD
- Tenofovir alafenamide PO QD

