- History (i.e., started prior to start of study treatment) of non-prescribed illicit injection drug use (yes, ongoing as of the end of study participation; yes, last dose after last dose of study treatment; yes, last dose during study treatment period; yes, last dose less than 6 months prior to start of study treatment; yes, last dose 6 to 12 months prior to start of study treatment; yes, last dose more than 12 months prior to start of study treatment; yes, timing of last dose unknown; or no);
- PWID Status Classification 1 with respect to study treatment start (current/recent PWID or former/non-PWID; current PWID, recent PWID, former PWID, or non-PWID);
- PWID Status Classification 2 with respect to study treatment period (current/recent PWID or former/non-PWID; current PWID, recent PWID, former PWID, or non-PWID);
- PWID Status Classification 3 with respect to study participation (current/recent PWID or former/non-PWID; current PWID, recent PWID, former PWID, or non-PWID);
- Baseline APRI ( $\leq 1, > 1$  to  $\leq 2$ , or > 2);
- Baseline FibroTest (< 0.75 or  $\geq$  0.75);
- Baseline FIB-4 (< 1.45,  $\ge 1.45$  to  $\le 3.25$ , or > 3.25);
- Baseline AST/ALT ratio ( $\leq 1 \text{ or } > 1$ );

- Risk behavior for acute HCV infection (shared drug-injection equipment, shared non-injection drug use equipment, unprotected sexual activity with multiple partners, unprotected sexual activity with other male(s), risky tattoos or body piercings, shared personal items possibly contaminated with blood, healthcare worker with occupational exposure, or other behavior);
- Grouped risk behavior for acute HCV infection (contaminated needle or IV drug use, contact with infected individual, occupational exposure, or other behavior);
- Grouped risk behavior for acute HCV infection (drug use, sexual transmission, contact by contaminated objects, occupational, other behavior);
- Baseline HCV/HIV co-infection status (HCV mono-infected or HCV/HIV-1 co-infected);
- Estimated acute HCV infection duration (< 3 months, ≥ 3 months to

   < 6 months, or ≥ 6 months) across all and by each acute HCV infection criteria used to estimate infection duration;

- History of prior HCV infection (yes or no);
- Baseline fibrosis stage (equivalent to Metavir F0 F1, F2, F3, or F4);
- Baseline cirrhosis status (cirrhotic, non-cirrhotic, or unknown test results indeterminate);
- Treatment duration (< 52 days or  $\geq$  52 days);
- Study treatment compliance (yes or no).

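### The SAP's estimated infection start date can contradict the subject's own qualifying evidence, chiefly under criterion (c), so affected subjects can be placed in the wrong infection-duration category

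*SAP*

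**What the plan says.** The labels (a) to (d) are those of SAP 7.1 for the four alternative proofs of acute infection in Protocol 5.1, criterion 5.

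- **Criterion (c), eligibility.** The subject needs ALT above 5 × ULN and/or jaundice, without any "history of chronic liver disease or other cause of acute hepatitis and positive HCV RNA or HCV core antigen all within an 8-month period" before Screening. Risk behaviour is also required, in the 6 months before the positive test. No maximum gap is set between the hepatitis and that test.
- **Criterion (c), dating.** For "acute infection criteria (c), estimated infection start date is defined as 6 weeks (42 days) prior to the date of the HCV positive test".
- **Criterion (d), dating.** "For acute infection criteria (d), estimated infection start date is defined as6 weeks (42 days) prior to the date" of the positive test. This criterion rests on a negative antibody together with a positive RNA or core antigen.
- **Criterion (a), dating.** "For acute infection criteria (a), estimated infection start date is defined as the midpoint between the HCV negative test and HCV positive test". The negative test may be antibody, RNA or core antigen. Criterion (b) is dated in the same way.
- **Choice of test.** On the positive side, "the earliest (i.e., furthest from study treatment start date) positive HCV test of those specified will be used".
- **Priority.** A subject who meets several criteria is dated by (d) first, then (a), then (b), then (c).
- **Use.** Duration is cut at 93 and 186 days, summarised at baseline (SAP 7.1), and used as an SVR12 subgroup (SAP 9.6) "across all and by each acute HCV infection criteria used to estimate infection duration".

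**The concern.** Under (c), the hepatitis is the evidence that the infection was acute, yet the infection is dated only from a virus test that may have been done much later. The estimate can therefore say that infection began after the illness accepted as its sign.

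Under (d), a subject may also hold a negative RNA or core antigen result and so meet (a) too. Because (d) ranks first, the fixed 42-day offset is used and can place infection before that negative result. Rule (a) would not allow this, since it treats the negative test as the earlier limit of the infection date.

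Estimated duration is the only SVR12 subgroup in SAP 9.6 defined by elapsed infection time; time since diagnosis appears only among the baseline characteristics. Protocol 2.1 treats 6 months as the point at which infection is considered chronic. Reporting a subject infected for more than 6 months as under 3 months therefore blurs the distinction that this trial studies. The two faults run in opposite directions: (c) understates duration and (d) overstates it.

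**Working it through.** **The plan's own figures.** 3 × 31 = 93 days, 6 × 31 = 186 days and 6 × 7 = 42 days; all agree with SAP 7.1. Duration = treatment start − estimated infection start + 1. Protocol Appendix D puts Screening 1 to 30 days before Day 1.

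**Assumption.** The SAP gives the 31-day month only for categorising duration. Applied to the 8-month window it gives 8 × 31 = 248 days.

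**Criterion (c).** Let *g* be the days from hepatitis to first positive test, *s* from that test to Screening, and *k* from Screening to Day 1.

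- SAP duration = *s* + *k* + 42 + 1
- Smallest duration consistent with the hepatitis = *g* + *s* + *k* + 1
- The estimated start falls *g* − 42 days after the hepatitis whenever *g* > 42.

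The maximum is 248 − 42 = 206 days, with hepatitis at the far end of the window and the first positive test at Screening. With 30-day months it is 240 − 42 = 198 days.

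| Case | *g* | *s* | *k* | SAP duration | Minimum consistent duration |
|---|---|---|---|---|---|
| Jaundice 217 days, positive test 7 days before Screening | 210 | 7 | 30 | 7 + 30 + 42 + 1 = 80 (< 3 months) | 217 + 30 + 1 = 248 (≥ 6 months) |
| Four-month gap | 124 | 0 | 15 | 0 + 15 + 42 + 1 = 58 (< 3 months) | 124 + 0 + 15 + 1 = 140 (3 to < 6 months) |
| Gap of exactly 42 days | 42 | 60 | 15 | 60 + 15 + 42 + 1 = 118 (3 to < 6 months) | 42 + 60 + 15 + 1 = 118 (same) |

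The first case moves two categories, the second moves one, and the third shows no conflict.

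**Criterion (d).** Let *g* be the days from the last negative RNA or core antigen test to the first positive, and *t* from that positive to Day 1.

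- SAP duration = *t* + 42 + 1
- Largest duration consistent with the negative test = *t* + *g* + 1
- Midpoint rule, as in (a) = *t* + *g*/2 + 1
- The estimated start precedes the negative test by 42 − *g* days whenever *g* < 42, so by at most 41 days (*g* = 1).

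Example with *g* = 14 and *t* = 60:

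- SAP: 60 + 42 + 1 = 103 days (3 to < 6 months)
- Largest consistent: 60 + 14 + 1 = 75 days (< 3 months)
- Midpoint: 60 + 7 + 1 = 68 days (< 3 months)

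The estimated start is 42 − 14 = 28 days before the negative test. With *g* = 14, the SAP category is too high when *t* + 43 reaches a cut point that *t* + 15 does not. That is *t* from 50 to 77 (cut at 93) or from 143 to 170 (cut at 186). Outside those ranges the category is unchanged.

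**The case against.** Much can be said for the plan:

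- **Reach of (c).** It is last in the priority order, so its rule dates only subjects who meet none of (d), (a) or (b). They also need a physician diagnosis of acute infection and no evidence of chronic infection. Using the earliest positive test narrows the gap further. A subject tested before the hepatitis, or within 42 days after it, shows no conflict. All this limits the number affected, but none of it sets a maximum gap.
- **Reporting by criterion.** This separates subjects dated by (c) or (d) from those dated by the midpoint, so methods are mixed only in the pooled rows. Within the (c) rows, an affected subject still sits in the wrong category.
- **Weakness of (d).** It needs an extra negative RNA or core antigen test in the six weeks before the positive, and it assumes that this negative excludes infection on that date. A negative antibody alone creates no conflict. The inconsistency with rule (a) stands, but it is a minor one.
- **Source of the rules.** The SAP says that its derivations were adapted from two published articles. Those were not available here, so whether this is an established convention cannot be judged. Even so, the conflict with the subject's own dates would remain.
- **Consequence.** The variable feeds a baseline table and one of many descriptive subgroups with Wilson intervals and no hypothesis test.

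A reader might infer that the duration subgroups are wrong as they stand, or that the reported SVR12 rate in early infection is contaminated. The documents do not support that: they give neither the number of (c) subjects nor the gaps between their hepatitis and first test. Nor do they show that the midpoint is in general the more accurate estimate for (d).

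**Conclusion.** The point holds as a flaw in the derivation rule. As written, SAP 7.1 permits start dates that the qualifying evidence rules out.

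- Under (c) the displacement can reach 206 days (198 with 30-day months) and two duration categories.
- Under (d) it is at most 41 days and one category.

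The (c) result assumes that the hepatitis belongs to the infection being treated, as the eligibility criterion itself does. The (d) result takes a negative RNA or core antigen test as the earlier limit of infection, as rule (a) does. How often either occurs is unknown.

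The primary and key secondary tests, their thresholds, the analysis populations and the sample size do not use this variable. The correction is worth making because it is cheap and removes impossible dates from the only SVR12 breakdown by infection time.

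**What to change.** Amend SAP 7.1 as follows.

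1. **Criterion (c).** Require the estimated start to be no later than the first documented qualifying date of ALT above 5 × ULN or jaundice. One way is to apply the existing 42-day offset to the earlier of that date and the first positive test. In the 80-day example this gives 217 + 30 + 42 + 1 = 290 days. The SAP uses the 42-day offset only from a positive test, so carrying it over to the hepatitis date is a choice. The bound itself is the minimum needed.
2. **Criterion (d).** Do not let the start precede the most recent negative HCV RNA or core antigen test before the first positive. Where it would, use the midpoint between that negative and the first positive. Exclude antibody negatives from this midpoint: criterion (d) itself accepts a negative antibody alongside detectable virus, so such a result does not bound the infection date.

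Then derive the baseline summary and the SVR12 duration subgroup from the amended date.

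The cost is a few lines of SAP text and code, with no new visits or subjects. The hepatitis date must be in the database or taken from eligibility source documents; the protocol and SAP do not show that it is recorded electronically. Where it cannot be found, keep the present rule for that subject and report how many subjects were dated that way.
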